There is evidence in the literature for altered nociception in patients with FM⁹. FM is also characterized by heightened pain sensitivity to sensory stimuli, possibly as a result of the changes in the central processing in the brain, referred to as central sensitization¹. From a mechanistic perspective, the abnormal efferent activity could be reflected in the affected skeletal muscle. Our study objective is to explore this possibility using image texture feature analysis in B-mode US imaging. We believe that this may be possible since we have previously shown that texture features can not only discriminate between healthy controls and patients with neck pain but also between the two clinical phenotypes of Myofascial Pain Syndrome (MPS), namely groups that contain latent and active myofascial trigger points (MTrPs)¹⁰. Towards this, we propose to use the image texture features to construct a regularized logistic regression model in order to predict and discriminate between healthy controls and fibromyalgia affected muscle.

To summarize, our specific research questions are as follows:

- a. Can a regularized logistic regression model, built on texture variables extracted from B-mode ultrasound images of the upper trapezius discriminate between healthy, and FM subjects? Our hypothesis is that the model should effectively differentiate the two cohorts due to our previous work/success with other chronic pain disorders (MPS).
- b. How does regularization impact the overall performance of the trained model? Our hypothesis is that it should improve its generalizability.
- c. Does the holdout, test data validate the predicted performance of the logistic regression model? Our hypothesis is that it will be within 1 standard error of the prediction mean.

Methods & Design

Study Design:

The study conforms to the Consolidated Standards of Reporting Trials recommendations.

Ethical approval is approved by the University Health Network (UHN) Research Ethics Board.

This study is registered under the National Institutes of Health ClinicalTrials.gov. This proposed study is a diagnostic case-control study with one major independent binary outcome measure (FM present or Healthy), to create 2 patient cohort groups.

Participants:

Recruitment

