The experimental protocol will be carried out in the MSK/pain specialty outpatient clinic at Toronto Rehabilitation Institute. Following the completion of the preliminary intake forms and participant debriefing, informed consent will be obtained. Each participant will be seated upright with their hands comfortably on their thighs in a chair that has a high supportive back. They will be asked to relax their neck and shoulder muscles. [name] will then apply the inclusion and exclusion criteria to the patient and assess entry into the study. A research associate, blinded to the clinical status of the study participant, will collect the ultrasound images using a Sonosite X-porte ultrasound system (SonoSite Canada Inc. c/o Visualsonics, [name]) at a depth of 3.0 cm or less and with a linear ultrasonic transducer of 6-15 MHz. The image settings such as depth, sector size, and time gain compensation (TGC), will be kept constant for all participants. The transducer will then be placed perpendicular on the upper trapezius muscle on each side, and its angle was adjusted to acquire the highest quality image. Ultrasound Gel will be used to coat the entire surface of the

transducer before it touched the skin surface. The location on the muscle will be standardized across study participants by being at the midpoint of the muscle belly between the C7 spinous process and the acromioclavicular joint. From that position, the transducer will be moved at a speed of approximately 1 cm/sec toward the acromioclavicular joint to obtain a 10-sec video. One video will be acquired from each side of the muscle group per participant.

Image Pre-processing

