All images pre- and post-processing will be performed with MATLAB and the image processing toolbox¹¹. Images will be visually and statistically inspected for quality based on image intensity, contrast, and ability to discriminate muscle fibers. This is necessary to maintain a high standard of imaging data quality, and suspect no more than 15% of the data should be removed due to constraints. Next, since we are analyzing ROI's in the muscle we must extract only a certain number of frames from each video series. We will achieve this using an image filtering method that has been previously used by our group called the CW-SSIM¹² filtering method¹³. It will be used to objectively calculate and extract image frames from each video series in order to obtain the maximal number of images, while still maintaining uniqueness (minimal image overlap). After this procedure is finished we will extract a rectangular ROI estimation of the upper trapezius muscle excluding the upper and lower fascial borders. Lastly, the images will be labelled and organized for further processing.

Feature Extraction

Texture variables will then be extracted from the image ROI's using MATLAB and the image processing toolbox. The features to be extracted are as follows:

1. First order histogram parameters associated with image grayscale. These include mean, standard deviation, skewness, and kurtosis.

2. Gray level co-occurrence matrices (GLCM)¹⁴ will be calculated utilizing 4 directions (0,45,90,135 degrees). 76 variables are then created.
3. Lastly run-length parameters¹⁵ will be determined by gray level run-length matrices based upon the four given directions. Averaging the directions together gives seven features.

In total 88 feature variables will be extracted from each ROI, providing a feature descriptor dataset.

Elastic Net Regularized Logistic Regression

We will then construct and train an elastic net regularized logistic regression model on the dataset using the binary class labels constructed earlier¹⁶. This will be done using MATLAB and the Statistics and Machine Learning Toolbox¹⁷ and performed on a train/test split (80/20) of the original training data. The model will be regularized using the elastic net, which will improve the generalizability of the classification model on unseen data (avoid overfitting problems). The elastic net penalization method also provides a form of variable selection helping to minimize the effect of rank deficiency.

Model Validation

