The model will be validated using 10-fold nested cross validation on the training data due to the fact the model needs hyper-parameter tuning alongside the validation process. This requires a nested procedure where the hyper-parameter tuning is done in an inner loop and the validation of the model is in an outer loop. This will allow for an optimized, trained model that should generalize well to unseen data. This generalization will be tested using the final holdout set and will either confirm or deny whether the constructed model is a good classifier for this task.

Results

After the methodology is applied to all training data, performance metrics can be extracted from the results to demonstrate the model efficacy. Performance metrics like sensitivity, specificity, area under the curve (AUC) and accuracy will be extracted in order to characterize the model performance. These metrics will be averaged across the 10-folds (mean + stdev), and these values will be compared to the final metrics extracted from the holdout test set. If the test set values fall within 1 stdev, it will confirm the accuracy of the performance estimation during the training.

Primary Outcome

The primary outcome measures:

1. Binary classifier discriminates effectively (>70 % accuracy) between the healthy and muscle with FM.
2. Impact of regularization on the model performance.
3. Holdout test validation of the predicted performance.

Discussion

The overarching goal of our research utilizing image texture features is to eventually provide diagnostic aid to clinicians through the usage of clinically feasible, objective and reliable quantitative ultrasound techniques. While computer aided diagnosis research in ultrasound has been heavily explored in areas such as cancer and liver diseases¹⁸⁻²⁰, there has been little to no work in chronic pain¹³. This is the basis for this project proposal utilizing logistic regression modeling with elastic net regularization; the objective is to develop a statistical model with good predictive and diagnostic capabilities.

We are using logistic regression as our classification model due to its efficiency, computational resource requirement, interpretability, input feature scaling invariance, and ease of regularization²¹. The fact that logistic regression intrinsically calculates the predictive probability is a major strength of the model, as other classification techniques require further computationally intensive cross-validation to achieve this.

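### The 80/20 split and the folds are not tied to the participant; split by ROI, as the dataset is laid out, accuracy is inflated and the holdout check cannot reveal it

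*Protocol*

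**What the plan says.** - **Data Acquisition:** "One video will be acquired from each side of the muscle group per participant", so each person contributes two videos.
- **Image Pre-processing:** the team will "extract only a certain number of frames from each video series", using a CW-SSIM filter that aims for as many frames as possible with little overlap. An ROI is then drawn and the images are labelled.
- **Feature Extraction:** "In total 88 feature variables will be extracted from each ROI, providing a feature descriptor dataset". This is the only dataset the protocol defines.
- **Elastic Net Regularized Logistic Regression:** the model is trained on that dataset, "performed on a train/test split (80/20) of the original training data".
- **Model Validation:** "The model will be validated using 10-fold nested cross validation on the training data". The holdout then decides whether the classifier is good.
- **Results:** "If the test set values fall within 1 stdev, it will confirm the accuracy of the performance estimation during the training".
- **Primary Outcome:** item 1 requires accuracy above 70%; item 3 is validation on the holdout.
- **Research question (a):** whether the model can "discriminate between healthy, and FM subjects".

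No section says whether the split and folds are drawn by ROI, by video or by participant. None combines the ROIs of one person.

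**The concern.** Rows and labels are both at image level, so splitting the dataset as described means splitting ROIs. Frames from one sweep, and the two sides of one person, share that person's tissue and carry the same diagnosis. The CW-SSIM filter limits overlap between frames; it does not make frames or sides of one person independent. A model trained on some of a person's ROIs and tested on the others can succeed by recognising the person, so the holdout is not unseen data in the sense the protocol relies on.

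Primary outcomes 1 and 3 both rest on these figures. The cross-validation folds and the holdout would contain the same leak and rise together, so agreement between them would be read as confirmation. The study could report a validated classifier when texture says nothing about fibromyalgia in a new person.

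**Working it through.** The protocol gives no sample size, number of frames per video or expected accuracy, so there is no planned figure to reproduce. Two things can be calculated.

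**1. Overlap between training and holdout.** The only input beyond the 80/20 ratio is m, the ROIs per person (assumed; m = 2 is one frame per video). If each ROI goes to training with probability 0.8:

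- share of participants in both sets = 1 − 0.8^m − 0.2^m
- share of holdout ROIs whose owner is also in training = 1 − 0.2^(m−1)

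| m | Participants in both sets | Holdout ROIs with owner in training |
|---|---|---|
| 2 | 1 − 0.64 − 0.04 = 32% | 1 − 0.2 = 80% |
| 4 | 1 − 0.4096 − 0.0016 = 59% | 1 − 0.008 = 99.2% |
| 10 | 1 − 0.1074 − 0.0000 = 89% | >99.9% |

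**2. Effect on accuracy when there is no fibromyalgia signal (true accuracy 50%).**

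*Main simulation.* Assumptions: 88 correlated features (12 latent factors plus noise), a participant random effect, no class effect, 1:1 groups, and elastic-net logistic regression (mixing 0.5) with the penalty tuned by 5-fold cross-validation. Settings: N = 40 or 80; m = 2, 4 or 10; within-person correlation 0.3, 0.5 or 0.7. There were 200 runs for each of the 18 settings (Monte Carlo error at most about ±7 points).

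- ROI split: mean holdout accuracy 0.54-0.93 overall, 0.54-0.65 at m = 2 and 0.60-0.86 at m = 4. The 70% threshold was passed falsely in 3% of runs (N = 80, m = 2, correlation 0.3) up to 100% (m = 10, correlation 0.7).
- Participant split: mean 0.49-0.51; false pass 0.5-9.5%.

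*Second simulation, different assumptions.* N = 40, 80 or 150; 6 or 12 ROIs per person; separate participant and side effects; correlation 0.3 or 0.6; independent features. A few settings (N = 40 or 80, 12 ROIs, correlation 0.6) were repeated with correlated features. With 8 runs per setting it is coarse.

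- ROI split, independent features: mean holdout 60-84%.
- ROI split, correlated features: mean holdout 60-74%.
- Participant split: mean holdout 42-51%.

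**3. Whether the one-standard-deviation check detects the leak.** Full nested cross-validation (10 outer, 5 inner folds) was run under the main simulation's assumptions at correlation 0.5, with 100 runs per setting (about ±10 points). The last two columns give the share of runs in which the fold mean exceeded 70%, the holdout exceeded 70%, and the holdout lay within 1 SD of the fold mean.

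| N / m | 1-SD check passed, ROI split | 1-SD check passed, participant split | All three met, ROI split | All three met, participant split |
|---|---|---|---|---|
| 40 / 4 | 71% | 78% | 41% | 0% |
| 40 / 10 | 83% | 71% | 83% | 0% |
| 80 / 10 | 84% | 75% | 71% | 0% |

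In the second simulation the check passed in 50-100% of runs with ROI splitting and 62-100% with participant splitting. Pass rates are similar with and without the leak.

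**The case against.** The strongest reply is that the protocol is silent rather than wrong. It never says the split is by ROI, and how folds are drawn could be left to an analysis plan. Some wording points towards participants: the groups are patient cohorts, the research question is about subjects, and the model is meant to generalise to unseen data. It is true that the unit is unnamed, and the sponsor may intend a participant split. But the protocol itself fixes the dataset, the split, the folds, the 70% criterion and the confirmation rule. The missing unit decides whether primary outcomes 1 and 3 can be interpreted, so it is not a detail that can safely be left elsewhere.

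The second reply is that the size is assumed. This stands in part. Inflation shrinks with more participants. At N = 150 and correlation 0.5, a further rough simulation (25 runs per setting) gave a mean ROI-split holdout of 0.62 with 4 ROIs per person (false pass 4-8%) and 0.67-0.69 with 10 ROIs (16-32%). At N = 80, 10 ROIs and correlation 0.5 it passed 70% in 68-96% of runs. False success is therefore not inevitable in every plausible design.

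Third, the 1-SD pass rates are too imprecise to show equality. Agreed: that the check cannot expose the leak follows from both estimates sharing it, and the simulated rates only agree with that.

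Finally, primary outcome 1 speaks of muscle, so scoring per participant is not dictated. That is so, but splitting by muscle would still allow a person's left side in training and right side in the holdout.

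**Conclusion.** The concern holds. The protocol does not make the participant the unit of the split and folds, and the only dataset it describes leads to splitting by ROI. The overlap figures follow from the 80/20 ratio and an assumed m. The bias is upward for any positive within-person correlation. Its size is illustrative: modest with one frame per video or with many participants, large with few participants and many frames. The plan seeks as many frames as it can get, which favours the larger end. Since the built-in holdout check shares the leak, a favourable result under an ROI split could not be interpreted for a new person. This should be corrected before the analysis is run.

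**What to change.** In Elastic Net Regularized Logistic Regression and in Model Validation, state that the holdout and every outer and inner fold are drawn by participant, stratified by fibromyalgia/healthy, with both sides and all frames of a person kept together. State also the unit at which accuracy, sensitivity, specificity and AUC are scored. One combined prediction per participant is a suitable choice given research question (a), but not the only one.

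The cost is a few lines of protocol text and code. No new data are needed, which matters because recruitment is already complete. Reported accuracy will probably be lower and more variable: in the simulation the fold SD was 0.11-0.18 with participant-level folds against 0.05-0.12 with ROI-level folds. If a participant split was always intended, one sentence settles the point.

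### The cross-validated metrics rest on one random 10-fold partition; repeating the nested cross-validation would cheaply reduce the fold-draw noise they carry

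*Protocol*

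**What the plan says.** In the section on elastic net regularized logistic regression, modelling is "performed on a train/test split (80/20) of the original training data". Under Model Validation, "The model will be validated using 10-fold nested cross validation on the training data", and "hyper-parameter tuning is done in an inner loop and the validation of the model is in an outer loop". Under Results, "These metrics will be averaged across the 10-folds (mean + stdev"), and the holdout is then compared with that summary: "If the test set values fall within 1 stdev, it will confirm the accuracy of the performance estimation during the training". Primary outcome 1 reads "Binary classifier discriminates effectively (>70 % accuracy) between the healthy and muscle with FM"; primary outcome 3 is the holdout validation of the predicted performance.

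The protocol mentions neither repeated partitions nor a random seed. It does not expressly exclude repeats, but an average over ten folds describes one partition, since R repeats would yield 10R fold values. It also does not name the estimate on which the 70% threshold is judged. The one sentence that assigns a decision on the classifier points to the holdout: "This generalization will be tested using the final holdout set and will either confirm or deny whether the constructed model is a good classifier".

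**The concern.** A nested cross-validation result depends on which units fall into which outer and inner folds, because the chosen penalty and the retained features change with the draw. With close to 90 correlated texture features and probably a modest sample, that dependence need not be negligible. It is separate from the sampling error of recruiting these participants rather than others, and it is the one part of the variance that computing alone can reduce. Recruitment is reported as complete under Trial Status, so more data are not on offer.

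Two primary outcomes could be touched. Outcome 3 compares the holdout with a fold mean and fold SD that both come from one draw. Outcome 1 is a bare threshold without an interval. If it is read on the cross-validated mean, the same images could fall above 70% under one seed and not under another.

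**Working it through.** **Inputs from the protocol.** Outer 10-fold loop with inner tuning (Model Validation); one 80/20 split; 70% threshold (Primary Outcome); 1-SD rule (Results). On predictors, "In total 88 feature variables will be extracted from each ROI", although the listed groups add to 4 + 76 + 7 = 87. The simulations used 87 or 88, a difference that does not matter here.

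**Assumptions, because the protocol gives no figure.** Training sizes of 40 to 160 independent units, balanced classes, correlated features, mean accuracy near 70%, an inner 5-fold loop, and one row per unit. There is no stated precision to reproduce.

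**Fold-draw noise.** Three simulations of this kind held each simulated data set fixed and redrew only the partition:

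| Run | Training n | SD from fold draw (points) | Share of variance | 70% verdict on cross-validation |
|---|---|---|---|---|
| A (30-40 data sets x 20 partitions) | 48, 80, 120 | 3.3, 2.6, 2.0 | 12-20% | two draws disagree in 17%, 14%, 21% |
| B (16 x 15) | 40, 80, 160 | 3.8, 2.6, 1.6 | 14%, 17%, 26% | mixed in 8, 11, 10 of 16 data sets |
| C (20 x 15) | 48, 80, 120 | 3.6, 2.7, 2.1 | 16-19% | two draws disagree in 26%, 20%, 20% |

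The shares in run B follow from its between-data-set SDs of 9.6, 5.8 and 2.7 points. At n = 80, for example, 2.6² / (2.6² + 5.8²) = 6.76 / 40.40 = 0.17. The last column applies only if the threshold is judged on the cross-validated mean.

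**Primary outcome 3.** In run C the holdout result (n = 12, 20, 30) was held fixed and only the partition was changed. The 1-SD verdict differed between two draws in 15%, 10% and 17% of cases, and 30-55% of data sets gave both verdicts.

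**What repetition buys.** With R repeats the fold-draw SD is divided by √R. For R = 50, √50 = 7.07, so 3.8, 2.6 and 1.6 points become 0.54, 0.37 and 0.23. With s the fold-draw share of the variance, the total SD is multiplied by √(1 - s + s/50) = √(1 - 0.98s):

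- s = 0.12: √0.8824 = 0.939, a reduction of about 6%.
- s = 0.26: √0.7452 = 0.863, a reduction of about 14%.

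**What it does not buy.** If 70% is judged on a holdout of 10, 20 or 40 units (run B's training sizes divided by 4), the binomial SE is √(0.7 x 0.3 / n) = 14.5, 10.2 and 7.2 points. Repeating the cross-validation does not change it.

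**Which SD after repetition.** In run B the mean between-fold SD was 21.4, 15.6 and 11.1 points, against 3.8, 2.6 and 1.6 between repeats. At n = 80, a band of ±2.6 points is 2.6 / 10.2 = 0.25 holdout SEs. Under a normal approximation that treats the cross-validated mean as exact, a holdout with identical true accuracy would fall inside it only about 20% of the time (2Φ(0.25) - 1 = 0.197).

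**The case against.** The strongest reply is that nothing here is wrong. A single run of nested 10-fold cross-validation is accepted practice, and the protocol correctly separates tuning from validation. The number of repeats and the seed are details that an analysis plan often supplies. Most of that stands, so this is an improvement and not a defect. It is still worth raising because the protocol itself fixes the summary as an average over ten folds.

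A reader might infer that the >70% verdict necessarily turns on the fold draw. The documents do not support that. Outcome 1 names no data set, and the Model Validation text points to the holdout, where the fold draw acts at most indirectly through the tuned penalty. The cross-validation reading has some support, since Results speaks of training-data metrics as showing efficacy and the holdout check is listed as a separate outcome, but it is not stated. A reader might also infer that repetition removes the noise. It only shrinks it, and 74 to 88% of the variance (100% minus 26% or 12%) is sampling error that it cannot touch.

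For outcome 3 it is fair to say that a shift of 2 to 4 points in the fold mean is small beside between-fold SDs of 11 to 21 points. Even so, run C shows that verdicts near the edge of the band do change.

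The sizes also rest on choices that favour the point. Accuracy was centred near 70%, where verdicts flip most easily. Classes were balanced, although the protocol expects imbalance. Each unit gave one row, although each participant gives two videos and may give several frames. If one participant's images were spread over folds, the noise would be smaller. The numbers of simulated data sets are small, so the disagreement rates are rough.

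**Conclusion.** The point holds as a cheap precision gain. On the natural reading of a single partition, the fold mean and fold SD that feed primary outcome 3 carry avoidable noise, and so does the verdict on primary outcome 1 if it is taken on cross-validation. The size is about 1.6 to 3.8 points SD, or 12 to 26% of the variance of the cross-validated accuracy, conditional on the assumed training sizes, class balance, signal and independence of units. The three simulations agree closely on the SD. Sampling error remains the larger part, and the single 80/20 split is unaffected.

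**What to change.** In Model Validation, state that the whole 10-fold nested cross-validation, inner tuning included, is repeated (for example 50 times) with new random partitions and a recorded seed, inside the 80% training data only. In Results, define the cross-validated accuracy, AUC, sensitivity and specificity as means over repeats.

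Add one clause to the 1-SD rule: the SD is the between-fold SD computed within each repeat and then averaged over repeats. It should not be the SD between repeats, which would narrow the band artificially. Research question c speaks of one standard error where Results uses one standard deviation, so the same clause should settle which is meant. Leave the holdout untouched.

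The cost is computing time and a sentence or two of text (a nested run took well under a second in simulation). No new data are needed.

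### Agreement within one fold SD does not confirm the cross-validated performance, and with few participants a pass on this rule says little

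*Protocol*

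**What the plan says.** The Protocol's section on the elastic net model sets aside a holdout, the work being "performed on a train/test split (80/20) of the original training data". Under Model Validation, "The model will be validated using 10-fold nested cross validation on the training data", with tuning in the inner loop. Results names four measures: "Performance metrics like sensitivity, specificity, area under the curve (AUC) and accuracy will be extracted". It continues: "These metrics will be averaged across the 10-folds (mean + stdev), and these values will be compared to the final metrics extracted from the holdout test". The decision rule follows: "If the test set values fall within 1 stdev, it will confirm the accuracy of the performance estimation during the training".

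This check is listed under Primary Outcome as item 3, "Holdout test validation of the predicted performance". It answers research question c, at the end of the section on the rationale for quantitative ultrasound, but there the yardstick differs: "Our hypothesis is that it will be within 1 standard error of the prediction mean".

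The Protocol states no number of participants or images, no expected performance, and no tolerance in accuracy points. It does not say whether one metric or all four must fall within the limit.

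**The concern.** The rule judges the gap between two estimates: one from the 20% holdout, the other a mean over the 80% training part. Its tolerance is the scatter of single folds. That scatter mainly reflects how few observations a fold contains, so a smaller study or a less stable model gets a wider limit. There is no ceiling on the disagreement that would still be accepted, and a gap too small to stand out is declared confirmation.

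The stake is the claim that the classifier's predicted performance has been validated. Primary outcome 1 is "Binary classifier discriminates effectively (>70 % accuracy) between the healthy and muscle with FM", so an overstatement from 65% to 75% would straddle the study's own threshold. If such an overstatement passes nearly as often as a correct estimate, a pass does not answer research question c.

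**Working it through.** The Protocol offers no figure to reproduce, so the check is of how the rule behaves.

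**Inputs from the Protocol.** 80/20 split, ten folds, four metrics. Each fold holds 0.80/10 = 0.08 of the data.

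**Assumptions, not in the Protocol.** N independent units (60, 100, 200 or 400), cross-validated accuracy p = 0.75, and an overestimate of d = 0.10 where one is examined. Folds are treated as independent.

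**Step 1, tolerance.** Fold SD = √[p(1−p)/(0.08N)], so its variance scales with 1/0.08 = 12.5.

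**Step 2, error of the quantity judged.** SE of holdout minus cross-validated mean = √[p(1−p)(1/0.2 + 1/0.8)/N], so its variance scales with 5 + 1.25 = 6.25.

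**Step 3, correct estimate.** Tolerance/SE = √(12.5/6.25) = 1.414 at any N. P(|Z| < 1.414) = 0.843. Simulation with the SD itself estimated from ten folds gives about 81 to 82%.

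**Step 4, estimate 10 points too high, accuracy alone.** Pass probability = Φ((SD + d)/SE) − Φ((d − SD)/SE). For N = 60: SD = √(0.1875/4.8) = 0.198 and SE = √(0.1875 × 6.25/60) = 0.140, giving Φ(2.13) − Φ(−0.70) = 0.741.

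| N | Fold SD | SE of difference | Pass if right | Pass if 10 points too high | Ratio |
|---|---|---|---|---|---|
| 60 | 0.198 | 0.140 | 0.84 | 0.74 | 1.1 |
| 100 | 0.153 | 0.108 | 0.84 | 0.68 | 1.2 |
| 200 | 0.108 | 0.077 | 0.84 | 0.54 | 1.6 |
| 400 | 0.077 | 0.054 | 0.84 | 0.33 | 2.5 |

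The last column is the pass rate of a correct estimate divided by that of the overestimate. It shows how weakly a pass separates the two.

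**Step 5, all four metrics required.** This was simulated with binormal scores, stratified folds and an assumed 60:40 mix. A correct estimate passes about 57 to 62% of the time. An accuracy falling from 75% to 65% passes about 44%, 37%, 26% and 14% of the time at N = 60, 100, 200 and 400. A separate run differed by one to three points.

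**Step 6, the one-standard-error version.** Read as SD/√10, the tolerance is 1.414/3.162 = 0.447 SEs, and P(|Z| < 0.447) = 0.345. A correct estimate then fails about two times in three. The two yardsticks differ 3.16-fold for the same question.

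**Step 7, several frames per participant.** With 10 frames each, intraclass correlation 0.1 to 0.5, splitting by participant and cross-validated accuracy 80% (all assumed), a correct estimate still passes about 81% of the time. One 10 points too high passes 42–63% of the time with 50 participants, 22–51% with 100 and 6–33% with 200. Extra frames help, by an amount the Protocol does not let one fix.

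**The case against.** A reader might infer that the rule accepts almost anything, or that an over-optimistic estimate is usually confirmed. The Protocol does not support either reading. It gives neither a sample size nor any size of optimism. At N = 400 the 10-point overestimate passes accuracy alone only about a third of the time. Results also speaks of test set values in the plural after naming four metrics, so requiring all four is a natural reading. On that reading the overestimate passes less than half the time at every N examined.

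Nor is the fold SD unrelated to sampling error. It is a constant 1.41 SEs of the relevant difference, which is stricter than a conventional 1.96-SE comparison. In the same model, that comparison would miss a 10-point drop about 89%, 85% and 74% of the time at N = 60, 100 and 200. Part of the weakness is therefore simply that a 20% holdout carries little information. This stands. It does not rescue the rule, because a comparison that cannot see a 10-point loss should not be reported as confirmation.

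Nested tuning already limits one source of optimism. If frames from one participant fell in both parts, which the Protocol neither states nor rules out, both estimates could share the optimism. That is a separate mechanism, and comparing the two parts would not reveal it under any rule.

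Finally, a strict margin has its own price. Requiring the lower 95% limit to exclude a 10-point loss would confirm a correct estimate with probability Φ(0.10/SE − 1.96), about 11%, 15% and 26% at N = 60, 100 and 200. That is a good reason not to prescribe that margin here.

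**Conclusion.** The point holds in a limited form. The one-SD rule is wrong as a criterion for confirmation: its width follows fold noise, it has no limit in accuracy points, and it turns a failure to see a difference into a positive finding. The 1.41-SE result needs no sample size, only independent units and the stated split and folds. How often an overestimate passes does depend on assumptions. At 60 to 200 units a 10-point overestimate passes on accuracy alone in 54 to 74% of cases, against 81 to 84% for a correct estimate, so a pass is weak evidence. With 400 units, many frames per participant, or all four metrics required, it passes less often.

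The contradiction with research question c is real, but choosing between the two yardsticks would not solve the problem. The criterion is written into the Protocol, so this is not a detail awaiting a SAP.

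**What to change.** - Delete the one-SD confirmation sentence in Results and the matching one-standard-error hypothesis in research question c.
- For each metric, report the holdout value and the holdout-minus-cross-validated difference, with 95% intervals from a bootstrap that resamples participants, not frames.
- Name one metric for primary outcome 3. Keep the fold SD as description only.
- Base the conclusion on the interval: state which losses it does not exclude, and do not call the estimate confirmed merely because no difference is seen. Any margin for confirmation is the sponsor's choice and should be fixed before the holdout is opened.

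The cost is a change of wording and a short bootstrap routine. No new data are needed, and Trial Status already records recruitment as complete. The drawback is that with a small holdout the result will often be inconclusive.
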